##### **7.5.3 Ancillary Endpoint Analysis**

Ancillary endpoints will be analyzed using the mITT analysis set.

- Clot Analysis**

- Histopathologic analysis of clot collected**

Subjects with any clot composition data (e.g., red blood cells, fibrin measurements) from at least one pass will be included into the clot analyses. Study passes without clots retrieved will be excluded from analyses. Missing data of clot dimension or composition from the central clot are anticipated to be very small. Missing data on clot composition or dimension will be excluded from analysis, should there be any.

Composition of clot components to be evaluated includes RBC, WBC, fibrin, collagen, platelets and Von Willebrand Factor (vWF), as evaluated from the Central Lab, will be summarized per pass and overall. The clot weight (mg) and area (mm^2) will also be summarized per pass and overall in same way.

The total area (across all passes with clots extracted and clot composition measured from central lab) will be calculated to sum up the area from all individual pass with clots. The total weight (across all passes) will be calculated in the same fashion as the total area.

The total amount of RBC (across all passes, %) in terms of area (A) =

$$RBC_{pass\ 1}(\%) \times \frac{A_{pass\ 1}}{Total\ A} + RBC_{pass\ 2}(\%) \times \frac{A_{pass\ 2}}{Total\ A} + \dots + RBC_{pass\ n}(\%) \times \frac{A_{pass\ n}}{Total\ A}$$

The total amount of RBC (%) in terms of weight (W) =

$$RBC_{pass\ 1}(\%) \times \frac{W_{pass\ 1}}{Total\ W} + RBC_{pass\ 2}(\%) \times \frac{W_{pass\ 2}}{Total\ W} + \dots + RBC_{pass\ n}(\%) \times \frac{W_{pass\ n}}{Total\ W}$$

Where  $RBC_{pass\ i}$  is the individual pass with RBC measurement; and n is the total number of passes with areas for that subject.

Other clot composition data (e.g., fibrin, white blood cells etc.) will be calculated in the same fashion as RBC, in terms of clot area and weight separately. All clot composition will be summarized per pass and overall across all passes. Additional analyses on clots may be performed as appropriate for exploratory purpose.

- Hospitalization Analyses**

Medical resource utilization and health economics related data will be summarized.

Hospitalization data will be summarized for alive subjects. Unscheduled hospitalizations post index procedure are considered as re-hospitalizations. The number of subjects who died during the index procedure or re-hospitalizations will be summarized separately.

Subjects with missing admission or discharge date for whom the calculation of length of stay cannot be performed will be excluded from calculation, e.g., withdrawal from study prior to discharge. However they will still be counted towards the number of index procedure hospitalizations and re-hospitalizations, as applicable.

- 1. Hospitalization length of stay for index procedure and unscheduled re-hospitalizations**

Summary statistics will include the total length of stay, length of stay in intensive care unit (ICU) and length of stay in medical/surgical floor or routine care, per the following formula:

- Length of stay (days) = date of discharge – date of admission + 1
- Total length of stay (days) = length of stay in ICU (days) + length of stay at medical/surgical floor or routine care.

Discharge location will be summarized for subjects who were discharged alive following index procedure.

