##### 1. Hospitalization length of stay for index procedure and unscheduled re-hospitalizations.

The mean, median, minimum and maximum duration of hospitalization length of stay will be summarized.

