#### **12.1.4 Health Economic Data**

Subject hospitalization information will be collected in the eCRF by the investigator and study-site personnel for all subjects throughout the study. Subject admission and discharge date will be collected for the index procedure. Re-hospitalization data for unscheduled events will include admission and discharge date and primary diagnosis, and all procedures performed during re-admission.

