## **2. Healthcare resource utilization for index procedure, post-procedure and re-hospitalizations for unscheduled events.**

The number and percentages of subjects with at least one re-hospitalization, the number of re-hospitalizations (including hospitalizations without discharge due to reasons such as death or early withdrawal ), and the mean and maximum length of stay will be summarized, where the maximum length of stay is taken to be the maximum stay, in number of days, across all re-hospitalizations at the subject level.

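### Length of stay is summarized from completed stays only, so the reported maximum can only be equal or too low, and the mean and upper quantiles may be too low as well

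*SAP*

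**What the plan says.** Protocol section 9.7.5.2 asks for simple summaries of the index stay and unscheduled re-hospitalizations: "The mean, median, minimum and maximum duration of hospitalization length of stay will be summarized". SAP section 7.1 adds the number of subjects, the standard deviation and the quartiles for continuous variables in general.

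SAP section 7.5.3 defines the measure as "Length of stay (days) = date of discharge – date of admission + 1", which cannot be evaluated without a discharge date. Its rule for such cases is "Subjects with missing admission or discharge date for whom the calculation of length of stay cannot be performed will be excluded from calculation", and its example is a subject who leaves the study before discharge. The next sentence keeps these subjects in the counts: "However they will still be counted towards the number of index procedure hospitalizations and re-hospitalizations, as applicable". The re-hospitalization item likewise reports "the number of re-hospitalizations (including hospitalizations without discharge due to reasons such as death or early withdrawal", next to the mean and maximum length of stay.

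Deaths are handled separately: "Hospitalization data will be summarized for alive subjects".

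On data collection, Protocol section 12.1.4 says "Subject admission and discharge date will be collected for the index procedure", and asks for the same dates for unscheduled re-admissions. SAP section 7.7 plans no imputation for length of stay, and the sensitivity analyses in section 7.8 concern only the mRS.

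**The concern.** The SAP treats a stay without a discharge date as ordinary missing data. If the date is absent because the subject was still an inpatient when observation ended, the stay is known to have lasted at least from admission to the last date in hospital. Protocol section 4.6.2 keeps data collected before withdrawal, where country rules allow, so that lower bound is usable. The SAP already uses this kind of information for mortality (section 7.5.2, item 6), where subjects without an event are censored at last contact.

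Whether a stay is dropped can depend on its length: the longer it runs, the more time there is for withdrawal or study exit to cut it off. The summary then describes completed stays rather than stays. At stake is the description of resource use, most of all at the upper end, together with a table in which the counts and the lengths rest on different sets of stays.

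**Working it through.** **The plan's own figures.** There is none for length of stay. The only design calculation is the margin of error for the primary endpoint, which reproduces: 1.96 × √(0.86 × 0.14 / 45) = 0.101. Its allowance of up to 10% attrition serves that endpoint and is not a forecast of withdrawal before discharge.

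**Maximum.** Completed stays are a subset of all stays, so their maximum cannot exceed the maximum over all stays. This needs no assumption.

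**Mean, if the dropped subject is a long stayer.** Assumptions: 50 subjects (the SAP's upper limit), a mean of 12 days among those discharged, admission on the procedure day, and k subjects still in hospital at day 90. By the SAP formula their stay is at least 90 − 0 + 1 = 91 days.

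Lower bound for the mean = ((50 − k) × 12 + 91k) / 50

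- k = 0: 12.0 days, no change
- k = 1: (588 + 91) / 50 = 13.58 days
- k = 2: (576 + 182) / 50 = 15.16 days

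The planned summary would report 12.0 in each case.

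**Mean, if the dropped subjects had short stays.** Suppose instead that k subjects withdrew early and would have had a stay of 5 days.

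- k = 1: (49 × 12 + 5) / 50 = 11.86 days
- k = 5: (45 × 12 + 25) / 50 = 11.30 days

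Here the planned 12.0 is slightly too high.

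**Simulation.** Each setting used 4,000 studies of 50 subjects, with log-normal stays (median 7 or 12 days, log-SD 0.8 or 1.1) and exit at day 90. Three withdrawal patterns were tried: none; 10% at times unrelated to length of stay; and 10% confined to stays below the median. All of these inputs are assumptions. Entries are the completed-stay summary minus the summary of the full eventual stays, in days.

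| Median, log-SD | Withdrawal | Mean number dropped | Mean | Q3 | Maximum |
|---|---|---|---|---|---|
| 7, 0.8 | none | 0.04 | −0.1 | 0.0 | −2.6 |
| 7, 0.8 | unrelated | 0.54 | −0.1 | −0.1 | −2.9 |
| 7, 0.8 | short stays | 5.05 | +0.6 | +0.8 | −2.5 |
| 7, 1.1 | none | 0.50 | −1.3 | −0.4 | −35.0 |
| 7, 1.1 | unrelated | 1.13 | −1.5 | −0.6 | −35.7 |
| 7, 1.1 | short stays | 5.52 | −0.4 | +0.9 | −34.8 |
| 12, 0.8 | none | 0.30 | −0.6 | −0.3 | −16.0 |
| 12, 0.8 | unrelated | 1.17 | −0.8 | −0.5 | −16.8 |
| 12, 0.8 | short stays | 5.27 | +0.4 | +1.1 | −15.0 |
| 12, 1.1 | none | 1.68 | −4.5 | −2.2 | −90.2 |
| 12, 1.1 | unrelated | 2.60 | −5.0 | −2.7 | −95.9 |
| 12, 1.1 | short stays | 6.66 | −3.1 | −0.1 | −91.1 |

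The maximum is low in every row. The mean and Q3 are low or level when withdrawal is absent or unrelated to length of stay, but can be too high when withdrawals had short stays. The shift in Q3 is under a day in most settings. The largest gaps in the maximum come from stays running well beyond day 90. No analysis of this study could recover those lengths, though it could show that they were unfinished.

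**The case against.** A reader might infer that the rule removes the longest stays and so biases the mean, Q3 and maximum downward. The documents do not support that. For withdrawals, the SAP's only example, all that is known is a lower bound, and such a subject may have been close to going home. No section describes anyone still in hospital at day 90. The unscheduled-visit window in Protocol section 6.6, which runs from discharge to the 90-day visit, suggests that discharge is expected before then. A discharge date can also simply go unrecorded. The certain direction therefore applies to the maximum alone.

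The exclusion is also pre-specified and partly visible. The number of subjects accompanies each continuous summary, so a reader could compare it with the count of hospitalizations. The planned median is little affected by a few long stays. The endpoint is ancillary and descriptive, with no hypothesis attached.

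All of this stands, and it limits the point to a small one. It does not remove it: a disclosed exclusion still discards a known lower bound, and a gap between two counts does not tell the reader how long the unfinished stays had already run.

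**Conclusion.** The point holds in limited form. Length of stay rests on completed stays, while the counts beside it include undischarged ones.

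- **Maximum:** equal or too low, whatever the withdrawal pattern.
- **Mean and upper quantiles:** expected to be too low if withdrawal is unrelated to length of stay; possibly too high if withdrawals had short stays.
- **All statistics:** unchanged if every subject is discharged within observation.

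The size cannot be derived from the documents. The rise from 12.0 to at least 13.6 days illustrates one day-90 inpatient among 50 under an assumed mean; it is not a prediction. Severity is low, since no primary or secondary endpoint is touched.

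**What to change.** Amend the hospitalization part of SAP section 7.5.3 as follows.

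1. For a stay with a known admission date and no discharge date, censor at the last date documented in hospital. Exclude a stay only if one of these two dates is unknown.
2. Report the number of undischarged stays, with the days in hospital so far for each.
3. For the total index stay, give the Kaplan-Meier median and quartiles of time to discharge. If subjects who die in hospital are brought into this analysis, treat in-hospital death as a competing event.
4. Show the maximum as '>= x days' when the longest stay is censored.
5. Label the existing mean, and the ICU, floor and re-hospitalization lengths of stay, 'among completed stays'. List undischarged re-hospitalizations with days to the last known in-hospital date.

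A mean restricted to day 90 is not advised. The 90-day visit may fall as late as day 104, so that horizon would cut off stays whose discharge was observed. For re-hospitalizations, the time left to day 90 also differs with each admission date.

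The cost is SAP wording and a little programming, since Kaplan-Meier is already planned for mortality. Admission dates are collected. Last contact does not by itself establish inpatient status, so the last in-hospital date may need a site query for each undischarged stay. Kaplan-Meier also assumes that censoring is unrelated to the remaining stay, which is why the individual listing matters. Reported stays may come out slightly longer, and the table needs a footnote.

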## **2. Healthcare resource utilization for index procedure, post-procedure and re-hospitalizations for unscheduled events.**

The number and percentages of subjects with at least one re-hospitalization, the number of re-hospitalizations (including hospitalizations without discharge due to reasons such as death or early withdrawal ), and the mean and maximum length of stay will be summarized, where the maximum length of stay is taken to be the maximum stay, in number of days, across all re-hospitalizations at the subject level.

### **7.6 Analyses of Adverse Events (AEs)**

The number of events, the number and percentage of subjects with at least one event will be summarized by body system organ class and preferred term using the latest version of Medical Dictionary for Regulatory Activities (MedDRA), overall and by following categories.

- All AEs
- Serious AE (SAEs)
- Device and/or procedure related AEs (composite)
- Device related AEs
- Procedure related AEs
- Unanticipated serious adverse device effects (USADEs)

### **7.7 Handling of Missing Data**

Missing data for the primary analysis of mRS  $\leq 2$  at 90 days (section 7.5.2) will not be imputed. The imputation of missing mRS scores at 90 days for sensitivity analysis is detailed in section 7.8.

There are no other missing data imputation planned in the study.

### **7.8 Sensitivity Analysis**

- mRS  $\leq 2$  at 90 days

Due to reasons other than all-cause mortality, missing mRS scores at 90 days (76 days or above) will be imputed using the last non-missing post-procedure mRS score (e.g., mRS score from discharge or any unscheduled visits) if available. If such

subjects have no post-procedure mRS scores, they will be excluded from sensitivity analysis.

The mRS  $\leq 2$  at 90 days will also be analyzed by the window of  $\pm 14$  days using observed data (without last observation carry forward imputation).

### 7.9 Subgroup Analysis

The primary endpoint will be analyzed by subgroups with clinically meaningful risk factors using the mITT analysis set. Additional subgroup analyses may be performed as applicable. Descriptive statistics (continuous summary measure for the mTICI score) for each subgroup will be presented when there is a minimum of 10 subjects in all subgroup levels, CIs will not be provided due to limited sample size.

- Clot composition: Tough clot vs. Other clot
- Nimbus first use: Procedural Pass 2 vs. Procedural Pass 3
- Vascular location:
- Balloon guide catheter (BGC) usage: BGC used vs. BGC not used

Subjects who used BGC are defined as those who used BGC at least once during procedure; otherwise subjects will be classified as no use of BGC throughout the procedure.

- Use of BGC and/or IC: BGC with IC, BGC without IC vs. no BGC
  - BGC with IC – subjects who used BGC and IC at least once during procedure;
  - BGC without IC – subjects who used BGC at least once, but none with IC during procedure;
  - No BGC – subjects who didn't use of BGC throughout the procedure.

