## 2 OBJECTIVES AND PURPOSE

The objective of this study is to assess the efficacy of NIMBUS in a real-world setting in patients where the first one or two passes with another Mechanical Thrombectomy therapy have not achieved mTICI 2b or better.

The rate of effectiveness achieved will be considered as we design further studies. The study will also report on clot characteristics and clinical outcomes.

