**Table 2: eTICI inclusive of the 2c rating**

eTICI (inclusive of the 2C rating) scale [31, 32, 33, 34, 35]	
0	No reperfusion; 0% filling of the downstream territory.
1	Thrombus reduction without any reperfusion of distal arteries.
2	2a Reperfusion in less than half (1-49%) of the territory. 2b50 Reperfusion in (50-66%) of downstream territory. 2b67 Reperfusion in (67-89%) of downstream territory. 2c Reperfusion in (90-99%) of downstream territory.
3	Complete or 100% reperfusion.

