## 7 Analyses to be Conducted

### 7.1 General Conventions

Descriptive summary statistics will be presented for all endpoints. The number and percentage of subjects will be summarized for categorical variables. Unless specified otherwise, percentages will be based on subjects with non-missing values. Descriptive statistics for continuous variables will include the number of subjects, mean, standard deviation, median, first quartile (Q1), third quartile (Q3), minimum and maximum. All statistical analyses will be performed using SAS® Studio, Version 9.4 or later.

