#### 7.5.1 Primary Endpoint Analysis

- **Successful Revascularization (mTICI  $\geq 2b$ ) with NIMBUS as determined by an Independent Core Lab.**

The primary endpoint is successful revascularization after the final pass of NIMBUS, where the successful revascularization is defined as an mTICI score of 2b or greater.

The number and percentage of subjects with a procedural mTICI score  $\geq 2b$  following the final pass of NIMBUS will be summarized, excluding mTICI scores from other devices applied after the final pass with NIMBUS.

Subjects with a missing mTICI score (from the imaging core lab) for the final pass using Nimbus, will be imputed with the final (end of procedure) mTICI score from the imaging core lab if the final pass using Nimbus is the last procedural pass, there were no post mechanical thrombectomy interventions and no intra-arterial thrombolytic agent performed after the final Nimbus pass.

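### SAP 7.9 promises the binary primary endpoint by subgroup, but the only statistic it names is a continuous summary of the ordinal, uncoded mTICI grade

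*SAP*

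**What the plan says.** SAP 7.9 opens with "The primary endpoint will be analyzed by subgroups with clinically meaningful risk factors", in the mITT set. It then names the statistic: "Descriptive statistics (continuous summary measure for the mTICI score) for each subgroup will be presented when there is a minimum of 10 subjects" in all levels of the subgroup. No confidence intervals are given, because of the small sample.

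The endpoint itself is defined elsewhere as a proportion. SAP 7.5.1 has "The number and percentage of subjects with a procedural mTICI score" of 2b or more after the final NIMBUS pass, leaving out scores from devices applied later. Protocol 9.7.4.1 also defines it by number and percentage.

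SAP 7.1 sets two conventions:
- Categorical variables: "The number and percentage of subjects will be summarized for categorical variables".
- Continuous variables: "Descriptive statistics for continuous variables will include the number of subjects, mean, standard deviation, median", and then quartiles, minimum and maximum.

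The grade is an ordered label (0, 1, 2a, 2b50, 2b67, 2c, 3). Protocol Table 2 attaches unequal reperfusion bands to the labels, for example "2b50 Reperfusion in (50-66%) of downstream territory" against 1-49% for 2a and 90-99% for 2c. Protocol 3.2.1 equates mTICI 2b with eTICI 2b50 as the threshold. Neither document gives numeric codes.

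For the balloon guide catheter (BGC) subgroup, SAP 7.9 says "Subjects who used BGC are defined as those who used BGC at least once during procedure". The split by BGC with or without IC (read here as intermediate catheter) uses the same whole-procedure rule.

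**The concern.** The endpoint announced and the statistic named do not match. A programmer who follows 7.9 literally would code the grades in some unstated way and print means, SDs and quartiles. The success rate need not appear, and it cannot be recovered from those summaries.

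The protocol says "The rate of effectiveness achieved will be considered as we design further studies" (section 2). If subgroup results are to help with that, they need to be on the same scale as the primary endpoint.

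There is a smaller problem in the catheter subgroups. The outcome is fixed at the final NIMBUS pass, but Protocol 6.3 allows another device or technique after the third NIMBUS pass. A catheter first used at that later stage still sets the subgroup. Later treatment is likelier after failure, so failures could move into the catheter-used group.

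**Working it through.** **The plan's own figure.** The only computed design figure treats the endpoint as a proportion. With p = 0.86 and n = 50 × 0.9 = 45, 1.96 × √(0.86 × 0.14 / 45) = 10.14%. This reproduces the 10.1% in Protocol 9.6 and SAP 6. The point here does not dispute it.

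**Step 1: does the result depend on the missing code?** Take two made-up levels of 10 subjects. Z has ten at 2b67 (100% success). W has six at grade 3 and four at 2a (60% success).

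| Assumed coding | Mean Z | Mean W |
|---|---|---|
| Ranks 0 to 6 | 4.0 | (6×6 + 4×2)/10 = 4.4 |
| Leading digit (every 2x = 2) | 2.0 | (6×3 + 4×2)/10 = 2.6 |
| Approximate midpoints of the Table 2 bands | 78 | (6×100 + 4×25)/10 = 70 |

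Two codings put W above Z although its success rate is 40 points lower. The third reverses that order.

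**Step 2: do the summaries determine the success rate?** Use codes 0 to 6, with success at code 3 or more, and two groups of 12:
- X: three at 2a, one at 2b67, four at 2c, four at 3. Success 9/12.
- Y: one at 2a, four at 2b50, one at 2b67, six at 3. Success 11/12.

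Both have sum 54 and sum of squares 272. So the mean is 54/12 = 4.5 and the SD is √((272 − 54²/12)/11) = √(29/11) = 1.62. With averaged empirical quantiles, both have Q1 3, median 5 and Q3 6, and both range from 2 to 6. Every SAP 7.1 continuous summary agrees while the success counts differ.

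The order can also be reversed by a wide margin. Nine at 2b50 and one at 0 give 90% success and mean 27/10 = 2.7. Eight at 3 and two at 2a give 80% success and mean 52/10 = 5.2.

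**Step 3: how often would the order reverse?** Two independent groups share one grade mix with 86% success, coded 0 to 6. The nine mixes combine three assumed failure splits over (0, 1, 2a) with three assumed success splits over (2b50, 2b67, 2c, 3):
- Failure: (.05, .03, .06), (.02, .02, .10), (.10, .02, .02).
- Success: (.215 each), (.10, .16, .20, .40), (.30, .30, .13, .13).

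The joint distribution of success count and code sum was enumerated exactly. The measure is the share of pairs with unequal success rates in which the mean difference has the opposite sign.
- 25 v 25 subjects: 0.115 to 0.213.
- 15 v 35 subjects: 0.170 to 0.263.

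In the 25 v 25 case, gaps of one or two successes supply 85% to 96% of the reversals. At a gap of four successes (4/25 = 16 points), the chance of reversal falls to 0.4% to 7%.

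**Step 4: the catheter rule.** Assume no true IC effect, 86% success, and half of BGC users with IC by the final NIMBUS pass. A share r of the failures without IC first get IC later. Successes are 0.43 in each group. Failures become 0.07(1 + r) with IC and 0.07(1 − r) without.

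| r | BGC with IC | BGC without IC | False gap (points) | Mean number moved among 25 BGC users (25 × 0.14 × 0.5 × r) |
|---|---|---|---|---|
| 5% | 0.43/0.5035 = 85.4% | 0.43/0.4965 = 86.6% | 1.2 | 0.09 |
| 10% | 0.43/0.507 = 84.8% | 0.43/0.493 = 87.2% | 2.4 | 0.18 |
| 25% | 0.43/0.5175 = 83.1% | 0.43/0.4825 = 89.1% | 6.0 | 0.44 |

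In whole subjects, start from two groups of 12 with 10 successes each. One moved failure gives 10/13 (76.9%) v 10/11 (90.9%), a gap of 14.0 points.

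**The case against.** The best defence is that number and percentage are already implied. SAP 7.9 announces the primary endpoint, which is a percentage, and SAP 7.1 gives n and % for categorical variables. The intervals that 7.9 declines to give would, under SAP 7.5, be exact intervals around a percentage. This is a fair reading, but it does not settle the matter. The parenthesis in 7.9 is specific and names another measure. Where the SAP wants counts by mTICI grade, as for the first-pass effect in SAP 7.10, it asks for them.

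The defence is stronger on size. The reversal figures assume equal true rates, so no true order is being reversed, and most reversals come from gaps of one or two subjects. Protocol section 2 speaks of the rate achieved in the study and does not mention subgroups, and the overall rate is fully specified with an exact interval. The protocol's statistical section plans no subgroup analysis at all.

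The catheter point is small. Protocol 1.3.6.1 places the guide or balloon guide catheter at access, so late first use is more plausible for IC than for BGC. The documents give no rate for it, and under the assumed rates fewer than one subject moves on average. The 14-point case largely shows how unstable groups near the 10-subject floor are.

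These objections limit the weight of the point. They do not make the named statistic the right one.

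**Conclusion.** The concern holds. SAP 7.9 states a rule that yields the wrong quantity for the endpoint it announces, and the rule cannot be programmed without codes that the plan does not supply. That the summaries fail to fix the success rate is shown by example and needs only one admissible coding. How often they would mislead (11% to 26% of unequal pairs) rests on the assumed codes, grade mixes and equal 86% rates, and falls quickly as the gap in successes widens.

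The catheter rule is a minor companion point that rests on assumed usage and switching rates.

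The practical harm is bounded. The section is descriptive, without tests or intervals, and the overall primary result does not change. It should be corrected because the defect is clear and the repair nearly free.

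**What to change.** In SAP 7.9, replace the continuous summary with a sentence to this effect: for each subgroup level, present n/N and the percentage with core-lab mTICI 2b or better after the final NIMBUS pass, as defined in SAP 7.5.1. Frequencies of the individual grades may be added. If a continuous summary is kept as well, state the numeric code for each grade.

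For the BGC and BGC/IC subgroups, count use only up to and including the final NIMBUS pass, from the per-pass records. Use at the first NIMBUS pass would be a stricter option. Catheter use over the whole procedure stays in SAP 7.4.

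The cost is SAP wording and minor reprogramming. Core-lab mTICI (Protocol 5.3) and ancillary devices (Protocol 6.3) are already collected per pass, so no new data are needed. One drawback is that some BGC/IC levels may fall below the 10-subject floor, in which case that subgroup would not be shown.

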Inclusion Criteria	
All Subjects:
 
 
1. Age <math>\geq</math> 18
 
2. The subject or the subject's legally authorized representative has signed and dated an Informed Consent Form.
 
3. Patient has had one or two passes of another mechanical thrombectomy device without achieving mTICI 2b or better and continues to have angiographic confirmation of a Large Vessel Occlusion (LVO) in the same vessel.
 

[figure not shown]
 A Large Vessel Occlusion (LVO) is an occlusion in the ICA, MCA, ACA, VA, or BA.

	
 
4. mRS 0-1 prior to this stroke.
 
5. NIMBUS is used on the second or third overall pass to attempt revascularization.
 

Exclusion Criteria	
 
1. Currently participating in an investigational (drug, device, etc.) clinical trial that may confound study endpoints. Patients in observational, natural history, and/or epidemiological studies not involving intervention are eligible.
 
2. Confirmation of positive pregnancy test according to site specific standard of care (e.g. test, verbal communication).
 
3. All patients with severe hypertension on presentation (SBP > 220 mmHg and/or DBP > 120 mm Hg). All patients, in whom intravenous therapy with blood pressure medications is indicated, with hypertension that remains severe and sustained despite intravenous antihypertensive therapy (SBP > 185 mmHg and/ or DBP > 110 mmHg).
 
4. Known cerebral vasculitis.
 
5. Known cancer with life expectancy less than 12 months.
 
6. Stenosis, or any occlusion, in a proximal vessel that requires treatment or prevents access to the site of occlusion.
 
7. Intracranial stenosis that prevents access to the site of occlusion.
 
8. Computed tomography (CT) or Magnetic Resonance Imaging (MRI) evidence of recent/ fresh hemorrhage on presentation.
 
9. Baseline computed tomography (CT) or MRI showing mass effect or intracranial tumor (except small meningioma).
 
10. Evidence of dissection in the extra or intracranial cerebral arteries.
 
11. Occlusions in multiple vascular territories (e.g., bilateral anterior circulation, or anterior/posterior circulation).
 

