## 4 Levels of Significance

No hypothesis tests are planned in the study. All confidence intervals will be reported at a two-sided 95% confidence level. These confidence intervals will not be used for statistical inferences, but for clinical reference purpose and are intended to convey precision in the estimates.

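### SAP 7.9 promises the binary primary endpoint by subgroup but specifies a continuous mTICI summary without confidence intervals, and drops a whole factor when one level has fewer than 10 subjects

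*SAP*

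**What the plan says.** SAP 7.5.1 defines the primary endpoint as a yes/no outcome: core-lab mTICI of 2b or greater after the final NIMBUS pass, summarised as a number and percentage. SAP 7.9 says this endpoint will be analysed by subgroup in the mITT set, and then sets three rules:

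- **Statistic.** "Descriptive statistics (continuous summary measure for the mTICI score) for each subgroup will be presented".
- **Display threshold.** Results are to be "presented when there is a minimum of 10 subjects in all subgroup levels, CIs will not be provided due to limited sample size".
- **Precision.** The second half of that same quote withholds confidence intervals and gives the small sample as the reason.

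The named factors include "Clot composition: Tough clot vs. Other clot" and "Nimbus first use: Procedural Pass 2 vs. Procedural Pass 3", balloon guide catheter (BGC) used or not, and a three-level split by BGC and IC use. Vascular location is also named, but its levels do not appear in the text available. No fallback is stated for a factor that fails the threshold.

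Elsewhere, SAP 4 says the study's confidence intervals are not for inference and "are intended to convey precision in the estimates". SAP 7.5 makes exact intervals around percentages the default unless instructed otherwise. SAP 7.1 lists what a continuous summary contains: number of subjects, mean, standard deviation, median, quartiles, minimum and maximum.

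**The concern.** Three features of one SAP passage work against its purpose.

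First, the statistic does not match the endpoint. mTICI is an ordered grade, and the primary endpoint cuts it at 2b. A mean, SD or median of grades does not give the proportion of successes in a level, so a table built to SAP 7.9 would not contain the quantity the section says it analyses.

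Second, small sample size is given as the reason for omitting intervals. If intervals exist to convey precision, as SAP 4 says, a small sample is where they carry most information. An exact interval remains valid at n=10.

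Third, the threshold applies to all levels of a factor together. A 41/9 split would show neither level, including the level of 41. The no-BGC group is a level in two of the named factors, so fewer than 10 such subjects would remove both.

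The split by first NIMBUS use is the one closest to the study objective, which covers patients in whom one or two passes had failed. The choice between the second and third pass is left to the physician (Protocol 6.3), so the split could be uneven. Protocol 2 says the rate achieved will be considered in designing further studies. A designer would want a rate and its uncertainty for each such group.

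**Working it through.** **Inputs.** Planned total up to 50 (SAP 1). Attrition of no more than 10%, giving 45 evaluable, and an assumed success rate of 86% (SAP 6). Display threshold of 10 in every level (SAP 7.9). Two-sided 95% intervals (SAP 4), exact by default (SAP 7.5). The documents give no subgroup shares, so these are assumed and varied.

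**Step 1: the plan's own figure.** 1.96 × √(0.86 × 0.14 / 45) = 10.14%, which matches the stated 10.1%. The plan gives no precision figure for any subgroup.

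**Step 2: chance that a two-level factor is displayed.** With X the count in the smaller level, X ~ Binomial(n, s), and display requires 10 ≤ X ≤ n − 10.

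| Smaller-level share s | n = 45 | n = 50 |
|---|---|---|
| 15% | 0.13 | 0.21 |
| 20% | 0.41 | 0.56 |
| 25% | 0.72 | 0.84 |
| 30% | 0.91 | 0.96 |
| 40% | 0.996 | 0.999 |

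Both columns matter. The threshold counts mITT subjects, of whom up to 50 are planned, while the precision calculation uses 45.

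**Step 3: three-level factor (such as BGC/IC).** Multinomial probability that all three counts reach 10:

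| Shares | n = 45 | n = 50 |
|---|---|---|
| Equal thirds | 0.89 | 0.96 |
| 50/25/25 | 0.48 | 0.68 |
| 50/30/20 | 0.35 | 0.52 |
| 60/20/20 | 0.13 | 0.27 |

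Three levels tolerate less imbalance than two.

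**Step 4: what an interval would show.** Clopper-Pearson 95% limits:

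| Successes/n | Exact 95% CI |
|---|---|
| 8/10 | 44.4% to 97.5% |
| 9/10 | 55.5% to 99.7% |
| 13/15 | 59.5% to 98.3% |
| 17/20 | 62.1% to 96.8% |
| 39/45 (whole cohort) | 73.2% to 94.9% |

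For 8/10 or 9/10, at the display threshold, the interval is 53 or 44 points wide, against about 22 points for the whole cohort.

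**Step 5: chance differences between levels.** If the true rate is 86% in both levels, the probability of an observed gap of 15 percentage points or more (exact enumeration of two independent binomials) is 0.22 for levels of 10 and 35, and 0.17 for 15 and 30 or for 20 and 25. This applies to percentages, which SAP 7.9 does not currently promise. It shows why percentages, once reported, should carry intervals.

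**The case against.** A minimum cell size is a common, prespecified convention. It depends on counts and not on outcomes, so it does not allow selection by result, and it guards against over-reading tiny groups. SAP 4 does not require an interval for every statistic, and SAP 7.5 allows exceptions, of which 7.9 is one. The protocol's statistical section plans no subgroup analysis of the primary endpoint, so this is exploratory output in a study with no hypothesis tests. SAP 7.9 also permits additional subgroup analyses, which leaves room for pooling. All of this stands. It limits the importance of the point and makes showing every very small level a matter of preference.

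A reader might infer three stronger things that the documents do not support:

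- **Bare percentages from about 10 subjects that look more certain than they are.** SAP 7.9 specifies a continuous summary, which under SAP 7.1 carries the number of subjects and the SD. Size and spread would be visible. The fault is that the success rate and its interval would not.
- **Vascular location can never be displayed.** Five levels of 10 need 50 subjects, and the protocol's definition of a large vessel occlusion "is an occlusion in the ICA, MCA, ACA, VA, or BA". But nothing links that eligibility footnote to the subgroup levels, which are absent from the available text and may have been lost in extraction or redacted. The SAP may use fewer levels, so no weight is placed on this.
- **Key splits will probably be suppressed.** At a smaller-level share of 30% or more, a two-level factor is displayed with probability of at least 0.91.

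The objection does not answer the mismatch between a binary endpoint and a continuous summary, the reason given for omitting intervals, or the missing fallback.

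**Conclusion.** The point holds as a modest reporting defect. The subgroup section does not report the endpoint it names, and it withholds intervals for a reason that sits badly with the purpose SAP 4 gives them. One sparse level would also hide adequate ones, with no stated alternative.

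The risk of suppression depends on shares that the documents do not give. For two-level factors it is serious at a smaller-level share of 20% or less (suppressed with probability 0.59 at n=45 and 0.44 at n=50 for a 20% share) and small at 30% or more (0.09 and 0.04). For three-level factors it is already substantial at 50/25/25 (0.52 and 0.32). These figures treat subjects as falling independently into levels with fixed shares.

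The primary estimate and its exact interval are unchanged. The change is worth making because it is cheap and the results are meant to inform later studies.

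**What to change.** Replace the display sentence in SAP 7.9. For each level of each named factor, report n/N, the percentage with mTICI 2b or better after the final NIMBUS pass, and the exact two-sided 95% confidence interval, labelled descriptive. A distribution of mTICI grades may be added but should not replace the percentage.

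If the minimum of 10 is kept, apply it level by level, so that adequate levels are still shown. Pool sparse levels where that makes sense, and state the pooling rule in advance.

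The cost is one SAP sentence and some wide intervals in the tables. No new data, visits or subjects are needed.
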